9.3.10 Incidence of Insertion of TIPS for Refractory Ascites

All occurrences of TIPS insertion are collected via a log through Month 12 and will be listed.

The number and percentage of subjects with at least one occurrence of TIPS insertion on or after treatment start date will be presented by treatment, and treatment differences will be analyzed using the same method as that for Incidence of disease-related complications. If a subject had at least one occurrence between screening and before the treatment start date it will be considered as a baseline occurrence. The odds ratio and corresponding 95% Confidence Interval (CI) will be determined from a logistic model, with the incidence of insertion of TIPS for Refractory Ascites (Yes/No) as the dependent variable and treatment, baseline occurrence, stratification factors of region (Europe or North America) as factors. Pre-hospitalization will not be included in the model as the subjects would be required to have been hospitalized to have an insertion of TIPS for refractory Ascites and this is considered as an exclusion criterion for the study.

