9.1.2.3 Exploratory Endpoints

As appropriate to the data, the original values or changes from baseline (last measurement taken prior to the start of study treatment on Day 1) of the following exploratory endpoints will be listed for each subject, summarized by treatment group, and compared between treatment groups by means of ANCOVA or Student's t tests (for normally-distributed variables), non-parametric Mann-Whitney U test (for non-parametric variables), Kaplan-Meier estimates and Log-rank test (for time-to-event variables), Poisson regression model (for count variables), and Fisher's exact test or Chi-square test (for binomial variables):

Incidence of ACLF, CLIF-C OF score, CLIF-C ACLF score, CLIF-C AD score, MELD score, Child Pugh score, number and length of hospital readmission for an acute complication of cirrhosis, number and length of ICU admission, incidence of disease-related complications, serum albumin concentration, albumin functional capacity (albumin binding capacity), incidence of insertion of TIPS for refractory ascites, and the EQ-5D-5L health questionnaire.

For the normally-distributed variables, the ANCOVA model will include change from baseline as the dependent variable, treatment as a fixed factor, and baseline value as a covariate. If any potential confounders are identified among subjects' baseline characteristics, they will be included as additional covariates in the ANCOVA models to adjust treatment effects. In addition, for the longitudinal measurements taken repeatedly over time, the treatment effects may be explored by using the mixed-effect model repeated measures analysis.

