6.2 Sample Size

Based on the CANONIC study, the overall 1-year transplant-free mortality rate in the current study population is assumed to be about 46% (11,16). Assuming a potential drop-out rate of 20% and 5% type-1 error for a 2-sided Chi-square test, a global sample size of 410 patients (205 per treatment group) will allow an 80% statistical power to detect an absolute reduction of 15% (17) for the 1-year mortality rate in subjects treated with SMT + Albutein 20%.

GRIFOLS	Number	IG1601	Version	2.0	Status	Effective	Effective Date	09-Sep-2024	Page	22 of 52
BIG-CL-SP-000319 IG1601 Statistical Analysis Plan										

GRIFOLS	Number	BIG-CL-SP-000319		Version	2.0	Status	Effective	Effective Date	09-Sep-2024	Page	23 of 52
	IG1601 Statistical Analysis Plan										

Alternatively, the sample size was calculated based on the log-rank test as follows. Assuming the 1-year transplant or mortality rate is 46% for the control group, or equivalently, the transplant-free survival rate is 54%, which translates to a hazard rate of 0.0017 assuming an exponential distribution. Using a log-rank test at the 2-sided significant level of 5%, a total of 125 events would provide at least 80% power to detect an absolute reduction of 15% in transplant or mortality rate (a 31% 1-year transplant or mortality rate, or equivalently, a 69% transplant-free survival rate) in subjects treated with SMT + Albutein 20%. This absolute difference in transplant or mortality rates translates to a hazard ratio of 0.6022, or an approximate 40% risk reduction. With all subjects followed for the entire 1-year duration of the study, a total of 322 subjects would be required to obtain 125 events. Assuming a dropout rate of 20%, a global sample size of 404 subjects (202 per treatment group) is required. This sample size calculation was performed using Proc Power with the two-sample survival statement in SAS version 9.4.

Taking a conservative approach, the larger of the 2 sample sizes (i.e., 410 subjects based on the Chi-square test) will be used to ensure the study has sufficient power.

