6.5 Hypothesis Testing and Multiplicity Adjustments

All statistical tests will be 2-sided with significance level fixed at 0.05.

The fixed-sequence testing method will be used to adjust for multiplicity in the analyses of the secondary efficacy endpoints (using the ITT population). Specifically, the superiority of SMT + Albutein 20% versus SMT alone for the secondary efficacy endpoints will only be tested if the superiority for the primary efficacy endpoint is demonstrated at the 2-sided significance level of 5% (for ITT population).

For the secondary efficacy endpoints, each subsequent hypothesis is tested only if the superiority for the previous comparison(s) listed below has been demonstrated at a 2-sided significance level of 5%. The order in which the null hypotheses will be tested is predetermined for the secondary efficacy endpoints as follows:

1. Time to death through 1 year after randomization
2. Time to liver transplantation or death through 6 months after randomization
3. Time to death through 6 months after randomization
4. Time to liver transplantation or death through 3 months after randomization
5. Time to death through 3 months after randomization
6. Total number of paracenteses
7. Incidence of refractory ascites according to the ICA criteria

No other adjustments for multiplicity are planned. P-values will be displayed for all the above pre-specified tests for completeness; interpretation and reporting of significant hypothesis test results will follow the fixed sequence approach described.

GRIFOLS	Bioscience Industrial Group	Number	IG1601	Version	2.0	Status	Effective	Effective Date	09-Sep-2024	Page	24 of 52
		IG1601	Statistical Analysis Plan								

7 Subject Disposition and Demographics

Unless otherwise noted, all demographics listings and summaries will be based on the ITT population. Subjects who were incorrectly stratified at the time of randomization will be listed and summarized.

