9.3.8 Incidence of Disease-Related Complications

GRIFOLS	Number	IG1601	Big-CL-SP-000319	Version	2.0	Status	Effective	Effective Date	09-Sep-2024	Page	38 of 52
	IG1601 Statistical Analysis Plan										

All disease-related complications will be collected via a eCRF through Month 12 and will be listed.

The number and percentage of subjects with at least one occurrence of each of the following disease-related complications from the list below on or after treatment start date will be presented by treatment, and compared using the generalized linear models implemented in SAS GENMOD procedure, in which the odds ratio and corresponding 95% Confidence Interval (CI) will be determined from a logistic model, with the incidence of disease related complication (Yes/No) as the dependent variable and treatment, stratification factors of region (Europe or North America) and history of hospitalization for acute decompensation of liver cirrhosis (yes or no) as factors. The robust variance estimate for the treatment effect will be estimated based on the compound symmetry working correlation structure. If the model does not converge, first-order autoregressive (AR (1)) working correlation structure will be used. If it fails to converge, the independent working correlation structure will be used.

Anticipated disease related complications will include:

- HE – including HE I, HE II, HE III, and HE IV
- GI Bleeding – including lower GI bleeding and upper GI bleeding
- Portal Hypertension
- Ascites
- Spontaneous Bacterial Peritonitis
- Hyponatremia
- HRS – including Type 1 and Type 2
- Other (includes disease related complications not captured in the types listed above)

In addition, the number of each type of disease-related complications will be counted for each subject and presented by treatment as a continuous variable and as a categorical variable with categories 0, 1, 2, 3, 4 or more. No analysis of treatment differences will be performed.

9.3.9 Serum Albumin Concentration and Albumin Functional Capacity in Serum (Albumin Binding Capacity)

Serum albumin concentration and albumin binding capacity are analyzed by a central laboratory, with all results and normal ranges reported in SI units. Serum albumin concentration is measured before and after each infusion at each visit during the treatment period; albumin binding capacity is measured once per visit.

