with onset date/time on or after the subject's randomization date/time for SMT arm, and with onset date/time during or after the first dose administration for the SMT + Albutein 20% arm. For subjects in the SMT + Albutein 20% arm, the first dose is scheduled on the same day as randomization. The definition is modified because the treatment time after randomization entered in the EDC for subjects in the SMT arm may not be on day 1, which may cause bias in the comparison of TEAE between the two groups. The new definition assumes that subjects in the SMT group had been on the SMT treatment before entering the trial. The new definition intends to remove bias in the comparison of TEAE between two treatment groups.

Changes in the analysis of longitudinal outcomes

The MMRM will be used to analyze the longitudinal continuous outcomes [e.g., CLIF-C OF score, CLIF-C ACLF score, CLIF-C AD score, MELD score, EQ-5D-5L index score, EQ-5D-5L VAS score], and general linear model implemented in SAS Proc GENMOD will be used to analyze the longitudinal binary or ordinal outcomes [Child-Pugh Score, Incidence of disease-related complications, Incidence of insertion of TIPS for refractory ascites]. However, as stated in Section 9.1.2.3 of the protocol, exploratory endpoints would be analyzed by means of ANCOVA or Student's t tests (for normally-distributed variables), non-parametric Mann-Whitney U test (for non-parametric variables), and Fisher's exact test or Chi-square test (for binomial variables). The methods specified in the protocol are not suitable for longitudinal outcomes with missing data.

Adding Ethnicity as a new subgroup analysis

The Ethnicity is collected in EDC. To account for any possible differential treatment effect based on ethnicity, a subgroup analysis will be done comparing Hispanic subjects vs non-Hispanic subjects. This subgroup analysis is incorporated in the appropriate sections above (see [Section 9.1.4](#)).

GRIFOLS	Number	BIG-CL-SP-000319	
	Version	2.0	
	Status	Effective	
	Effective Date	09-Sep-2024	
	Page	46 of 52	

13 References

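### TIPS insertion and disease-related complications are one yes/no per subject but carry repeated-measures variance text, and the plan has no usable interval if exactly one arm has no events (minor, exploratory)

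*SAP*

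**What the plan says.** SAP 9.3.8 reduces each complication type to whether a subject had at least one occurrence on or after treatment start. The yes/no result is modelled by logistic regression in GENMOD with treatment, region and hospitalization history as factors, and an odds ratio with 95% CI is reported. On the variance it says: "The robust variance estimate for the treatment effect will be estimated based on the compound symmetry working correlation structure". If the model fails to converge, the working correlation changes to AR(1) and then to independence.

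SAP 9.3.10 defines TIPS insertion in the same subject-level way and states that "treatment differences will be analyzed using the same method as that for Incidence of disease-related complications". Its factors are treatment, baseline occurrence and region.

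Protocol 9.1.2.3 had planned Fisher's "exact test or Chi-square test (for binomial variables") for exploratory endpoints of this kind. SAP section 12 replaces those tests. It groups both endpoints with the longitudinal binary or ordinal outcomes and gives the reason: "The methods specified in the protocol are not suitable for longitudinal outcomes with missing data".

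Neither 9.3.8 nor 9.3.10 has a rule for empty or sparse cells.

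**The concern.** A working correlation describes dependence between repeated records on the same subject. With one record per subject there is no such dependence, so compound symmetry, AR(1) and independence are the same model, and the three-step fallback changes nothing.

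What remains is a robust (sandwich) variance on a subject-level logistic model. That is harmless when both arms have events. When one arm has none, the estimated log odds ratio diverges while the robust standard error stays small, so the interval can look precise on almost no data. At stake is how an uncommon event, possibly TIPS or an uncommon complication type, is reported in the exploratory results.

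**Working it through.** **Inputs.** SAP 6.2 gives "a global sample size of 410 patients (205 per treatment group"). SAP 6.5 says "All statistical tests will be 2-sided with significance level fixed at 0.05". The documents give no expected TIPS or complication rate, so incidence below is an assumption shown over a range.

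**Arm size reproduced.** SAP 6.2 says "the overall 1-year transplant-free mortality rate in the current study population is assumed to be about 46"%, with a 15-point reduction, 80% power and this basis: "Assuming a potential drop-out rate of 20% and 5% type-1 error for a 2-sided Chi-square test". With pooled p = (0.46 + 0.31)/2 = 0.385:

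n = [1.960·√(2·0.385·0.615) + 0.842·√(0.46·0.54 + 0.31·0.69)]² / 0.15² = 164.0 per arm

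Power at 164 per arm is 0.79998, and 328/0.80 = 410. So 205 per arm is used below.

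**Robust variance with an empty arm.** With one record per subject, the sandwich variance of an arm's log-odds is Σ(y − p)² / [n·p(1 − p)]², where p is the fitted probability.

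- Arm with k events, p = k/205: this is 1/[205·p(1 − p)], the usual value.
- Empty arm, p running to 0: n·p²/[n·p(1 − p)]² tends to 1/n = 1/205. The model-based variance 1/[n·p(1 − p)] goes to infinity instead.

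For 0 versus 1, robust SE = √(1/205 + 205/204) = √(0.00488 + 1.00490) = 1.005. The fitted log odds ratio keeps falling until the software stops, so the interval excludes 1 once it passes −1.96 × 1.005 = −1.97.

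**Fitted check.** A binomial GEE with one record per subject and robust SE (not SAS) gave, for 0 versus 1, log odds ratio −21.25, SE 1.005, 95% CI for the odds ratio 8.3e-11 to 4.2e-9. Compound symmetry (exchangeable), AR(1) and independence gave identical results. With region added (80% Europe assumed), the log odds ratio was −21.18 and the SE 1.006. In step-by-step logistic fitting the interval already excluded 1 at iteration 6 (log odds ratio −6.70, CI 1.7e-4 to 8.8e-3). The model-based SE was about 31,000 at a log odds ratio of −20.7, so an ordinary Wald interval would include 1 but say nothing.

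**The protocol's tests on the same tables.** For 0 versus k, Fisher p = 2·C(205,k)/C(410,k), capped at 1, and the uncorrected chi-square statistic is 410k/(410 − k).

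| Events | Robust SE | Fisher p | Chi-square p |
|---|---|---|---|
| 0 vs 1 | 1.005 | 1.00 | 0.32 |
| 0 vs 2 | 0.714 | 0.50 | 0.16 |
| 0 vs 3 | 0.586 | 0.25 | 0.082 |
| 0 vs 4 | 0.510 | 0.12 | 0.044 |

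The exact conditional 95% CI for 0 versus 1 is 0 to 39.0.

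**Both arms with events.** For 1 versus 2, the odds ratio is 0.50 with robust CI 0.045 to 5.53. For 1 versus 4, the odds ratio is (1·201)/(4·204) = 0.246, SE = √(1 + 1/204 + 1/4 + 1/201) = 1.122, CI 0.027 to 2.22. Both are ordinary.

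**How often, with no treatment effect.** At true incidence π in both arms, let q = (1 − π)^205. The chance that exactly one arm is empty is 2q(1 − q). The last column counts every such table as excluding 1 and adds tables with events in both arms where the Wald interval excludes 1.

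| π | q | Exactly one arm empty | CI excludes 1 |
|---|---|---|---|
| 0.5% | 0.358 | 46% | 46% |
| 1% | 0.127 | 22% | 22% |
| 1.5% | 0.045 | 8.6% | 9% |
| 2% | 0.016 | 3.1% | 4.2% |
| 3% | 0.002 | 0.4% | 2.9% |

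The last column crosses 5% at about π = 1.9%, or 205 × 0.019 ≈ 3.9 expected events per arm.

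**The case against.** Much of the opposing case stands.

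- **Likelihood.** The complications in SAP 9.3.8 are the expected sequelae of this disease and several are pooled (all grades of HE, upper and lower GI bleeding, both HRS types). Protocol 4.4.1.2 makes TIPS part of standard care for several indications. A reader might infer from the 46% and 22% that the plan has a high false-positive rate. The documents do not support that: they give no incidence, and at 2% or more the rate is below 5%.
- **Software.** GENMOD was not run. With separation it may warn or return nothing, so it cannot be said that the trial's output will show an interval excluding 1. Without an estimate, though, the written fallback still offers no analysis.
- **TIPS wording.** The odds-ratio sentence in 9.3.10 says only that a logistic model is used; the robust variance comes in through the shared method. Read as ordinary logistic regression, the interval would include 1 and be uninformative.
- **Comparator.** A reader might infer that the SAP gave up a safe Fisher test for nothing. The protocol also allows chi-square, which gives p = 0.044 at 0 versus 4, and the SAP model adds covariate adjustment and an odds ratio with CI.
- **Consequence.** Both endpoints lie outside the fixed sequence in SAP 6.5. Counts by arm are shown alongside, so an odds ratio near 1e-9 would look degenerate to most readers.

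These points limit the size of the problem. They do not supply a reason for the working-correlation text or a method for an empty arm.

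**Conclusion.** The specification fault is clear from the text: two subject-level outcomes are labelled longitudinal and given a working correlation and fallback chain that cannot do anything. The numerical fault is conditional. It arises only when exactly one arm has no events; then either a printed robust 95% CI excludes 1 on as little as 0 versus 1 of 205, or no estimate is available and the fallback does not help. It does not extend to sparse tables in which both arms have events.

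This rests on one record per subject, about 205 per arm, and robust variance applying to TIPS through the shared method. An empty arm is plausible only below about 2% true incidence per arm, which the documents neither state nor rule out. Primary and secondary conclusions are untouched. Priority: minor.

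**What to change.** In SAP 9.3.8 and 9.3.10, delete the robust-variance and working-correlation sentences, including the fallback chain. Specify logistic regression on one record per subject with the covariates already listed, fitted with the Firth penalty and reported with a profile-likelihood 95% CI. Make this the single pre-specified method, or at least the rule whenever an arm has zero events. In section 12, remove these two endpoints from the longitudinal list and give covariate adjustment as the reason for departing from the protocol's tests.

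For a two-arm table without covariates, the Firth estimate equals adding 0.5 to each cell. At 0 versus 1 the odds ratio is (0.5 × 204.5)/(1.5 × 205.5) = 0.33, which is finite. A simple Wald interval on the same corrected counts runs from 0.013 to 8.19 and includes 1, as it should.

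The cost is SAP wording and a few lines of code, with no new data. The downside is slight shrinkage of the odds ratio.

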4.3.2 Randomization

Subjects who satisfy the inclusion criteria and who do not present any of the exclusion criteria will be enrolled in the study. Randomization must occur within 72 hours (3 days) of Screening. Randomization will be stratified by region (Europe or NA) and by whether or not subjects have been previously hospitalized for acute decompensation of liver cirrhosis prior to the most recent hospitalization for acute decompensation of liver cirrhosis with ascites as required by Inclusion Criterion #3v4 (Section 5.1). Within each stratum (ie, each unique combination of region and history of hospitalization for acute decompensation of liver cirrhosis), subjects will be randomly assigned to 1 of 2 treatment groups (SMT + Albutein 20% versus SMT alone) in a 1:1 ratio. Randomization will be centralized and will be performed via an Interactive Web Response System after subject inclusion. A computer-generated randomization list will be used for treatment allocation.

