5.2 Exclusion Criteria

A subject meeting any of the following exclusion criteria is NOT eligible for participation in the study.

1v5. Subjects with ACLF at Screening.

87 Ъ 24-Sep-2020 30 Effective Date Page Effective
 Number
 GLB-PRT-ALB-IG1601
 Version
 6.0
 Status
 Errect

 IG1601 - Prevention of Mortality with Long-Term Administration of Human Albumin in Subjects with
 6.0
 Status
 errect
Version 6.0 Decompensated Cirrhosis and Ascites GRIFOLS **Bioscience Industrial Group**

- 2v5. Subjects with type 1 HRS currently on treatment with vasoconstrictors or hemodialysis.
- 3. Subjects with TIPS or other surgical porto-caval shunts.
- 4v5. Subject with refractory ascites as defined by ICA criteria without any other event of acute decompensation (Appendix 2).
- 5v5. This criterion has been removed from protocol Version 5.
- 6v5. Subjects receiving dual anti-platelet therapy or anti-coagulant therapy (exception: DVT prophylaxis).
- 7v5. Subjects with ongoing endoscopic eradication of esophageal varices with ≤ 2 endoscopic sessions completed before screening.
- 8v5. This criterion has been removed from protocol Version 5.
- Subjects with evidence of current locally advanced or metastatic malignancy. Subjects with hepatocellular carcinoma within the Milan criteria [1 nodule ≤5 cm or 3 nodules ≤3 cm] [Appendix 6], non-melanocytic skin cancer, or controlled breast or prostate cancer can be included.
- 10v4. Subjects with acute or chronic heart failure (New York Heart Association [NYHA] Appendix 7).
- 11. Subjects with severe (grade III or IV) pulmonary disease (Global Obstructive Lung Disease [GOLD] Appendix 8).
- 12v5. Subjects with nephropathy with renal failure with a serum creatinine $\geq 2 \text{ mg/dL}$ or systemic hypertension.
- 13v5. This criterion has been removed from protocol Version 5.
- 14. Subjects with severe psychiatric disorders.
- 15. Subjects with a known infection with human immunodeficiency virus (HIV) or have clinical signs and symptoms consistent with current HIV infection.
- 16. Females who are pregnant, breastfeeding, or, if of childbearing potential, unwilling to practice effective methods of contraception (oral, injectable, or implanted hormonal methods of contraception, placement of an intrauterine device (IUD) or intrauterine system, condom, or occlusive cap with spermicidal foam/gel/cream/suppository, male sterilization, or true abstinence*) throughout the study.

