7.2.1.2 Treatment Period (Day 1 through Month 12)

7.2.1.2.1 **TREATMENT DAY 1**

Randomization must occur within 72 hours of screening, and it can occur while the subject is hospitalized of after discharge from the hospital. The first dose of Albutein 20% is administered on the same day as randomization. All assessments and activities will be performed prior to treatment. In the SMT + Albutein 20% treatment group, vital signs and serum albumin concentration will also be recorded after treatment. Study assessments and activities will include:

- Randomization (after confirmation of subject eligibility, hospital discharge (if applicable), and prior to treatment)
- Record vital signs (systolic and diastolic blood pressure [BP], heart rate [HR], respiratory rate [RR], temperature [T]) (measured immediately prior to and immediately after the end of the Albutein 20% administration in the SMT + Albutein 20% treatment group)
- Ascites assessment according to the ICA criteria (Appendix 2)
- Record weight
- Blood sample collection for (see Table 7-1):
 - Clinical laboratory assessments (eg, hematology, chemistry, coagulation)
 - Serum albumin concentration (measured immediately prior to and immediately after the end of the Albutein 20% administration in the SMT + Albutein 20% treatment group)
 - Systemic inflammatory assessment
 - Albumin functional capacity assessment (albumin binding capacity)
 - Blood biomarker retains (all clinical blood samples will need to be drawn first)
- Record concomitant medications
- Quality of life assessment (EQ-5D-5L health questionnaire [Appendix 5])
- Record AEs
- Albutein 20% infusion (SMT + Albutein 20% treatment group only)

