6.3 Randomization and Blinding

This is an open-label study. Subjects will be randomized into one of two groups (SMT + Albutein 20% versus SMT alone) in a 1:1 ratio based on a computer-generated randomization schedule. Randomization of subjects will be stratified by region (Europe or North America) and by whether or not subjects have been previously hospitalized for acute decompensation of liver cirrhosis prior to the most recent hospitalization for acute decompensation of liver cirrhosis with ascites as required by Inclusion Criterion #3v4. Within each stratum (i.e., each unique combination of region and history of hospitalization for acute decompensation of liver cirrhosis), eligible subjects will be randomized in a 1:1 ratio into 1 of 2 treatment groups.

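### The TIPS model in SAP 9.3.10 omits a randomization stratum for a reason that does not apply, and adds a baseline-TIPS term that is nearly empty

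*SAP*

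**What the plan says.** Protocol 4.3.2 sets two strata: "Randomization will be stratified by region (Europe or NA) and by whether or not subjects have been previously hospitalized" for acute decompensation before the index admission. SAP 6.3 repeats this.

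SAP 9.3.10 says that treatment differences in TIPS insertion are analysed by the method used for disease-related complications (SAP 9.3.8). That model contains treatment, region and history of hospitalization. SAP 9.3.10 then lists different terms for TIPS: "treatment, baseline occurrence, stratification factors of region (Europe or North America) as factors". It adds that "Pre-hospitalization will not be included in the model", on the ground that a subject must have been hospitalized to receive a TIPS and "this is considered as an exclusion criterion for the study".

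The baseline term is defined as follows: "If a subject had at least one occurrence between screening and before the treatment start date it will be considered as a baseline occurrence".

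On eligibility, protocol exclusion 3 reads "Subjects with TIPS or other surgical porto-caval shunts". Protocol 7.2.1.2.1 places randomization after eligibility has been confirmed, and has the first infusion on the day of randomization.

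**The concern.** Two terms in the prespecified model look wrong. The factor removed is a two-level randomization stratum, and the reason given for removing it concerns something else, namely whether the subject already has a TIPS. The factor added describes a state that the eligibility criteria are meant to prevent.

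The stakes are modest. The analysis would not condition on one of the factors by which subjects were allocated, a mistaken rationale in an effective SAP would carry into the study report, and one model parameter would go to a term that carries almost no information.

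**Working it through.** The documents give no figure on this point, so there is none to reproduce. The check compares the texts and adds two short calculations under assumed rates.

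**1. Which factor is dropped.** SAP 9.3.8 has treatment, region and history of hospitalization. SAP 9.3.10 has treatment, baseline TIPS and region. The missing one is history of hospitalization, so that is what the pre-hospitalization label must mean. The SAP revision history (item on Section 9.3.10) shows that the removal was deliberate and gives no further reason.

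**2. Does the reason apply?** The exclusion that SAP 9.3.10 refers to can be read in two ways.
- If it means hospitalization, there is no such exclusion. The index hospitalization is required by inclusion criterion 3v5, and an earlier one is a yes/no stratum.
- If it means TIPS, exclusion 3 does bar an existing TIPS or shunt. That does not determine whether the subject had an earlier admission for decompensation.

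Neither reading makes the stratum constant or irrelevant.

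**3. How the baseline term can be non-zero.** An existing TIPS is excluded, eligibility is confirmed before randomization, and dosing is due the same day. Two main routes remain:
- an eligibility violation that stays in the ITT population;
- a TIPS placed after randomization but before a delayed first infusion. SAP 9.3.6 defines treatment start as randomization for SMT alone but as first infusion for the albumin group, so this route exists in the albumin arm only.

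**4. What the term does, by number of such subjects (410 planned).**
- None: the columns are intercept, treatment, region and a column of zeros. The rank is 3 of 4, the coefficient cannot be estimated, and software would drop it. With history of hospitalization in its place the rank is 4 of 4.
- One: the indicator belongs to that subject alone, so the fitted probability goes to the observed outcome and the likelihood contribution goes to 1. The other coefficients are those obtained by deleting the subject. In effect the subject leaves the treatment comparison, whatever the outcome.
- Two: the same happens to both if they share an outcome, with probability p² + (1 − p)². Applying assumed TIPS rates to these subjects:
  - p = 0.05: 0.0025 + 0.9025 = 0.905
  - p = 0.10: 0.0100 + 0.8100 = 0.820
  - p = 0.15: 0.0225 + 0.7225 = 0.745

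**5. Effect of omitting the stratum on the odds ratio (OR).** Assume half the subjects have a prior hospitalization, balanced between arms. The marginal OR compares the average risks over the two strata.

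Example with control risks 0.0800 and 0.1481 (history OR 2) and a conditional treatment OR of 0.50:
- treated risks: 0.0417 and 0.0800
- average risks: 0.1141 control, 0.0608 treated
- marginal OR = (0.0608/0.9392) / (0.1141/0.8859) = 0.0648/0.1288 = 0.503

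Marginal OR across the assumed range, when the true OR is 0.50:

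| Overall control rate | History OR 1 | 2 | 3 | 5 |
|---|---|---|---|---|
| 5% | 0.500 | 0.501 | 0.503 | 0.506 |
| 10% | 0.500 | 0.503 | 0.506 | 0.511 |
| 15% | 0.500 | 0.504 | 0.509 | 0.517 |

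A true OR of 0.70 reads 0.700 to 0.714 over the same grid.

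**The case against.** The best defence is that little depends on this. TIPS insertion is exploratory and outside the fixed sequence in SAP 6.5, the removal is disclosed, and the odds ratio hardly moves. If TIPS events are few, leaving out a covariate is a reasonable economy, since a stratum level with almost no events could be hard to estimate. The low stakes stand. The economy argument would be legitimate, but the SAP does not make it, and the model spends the same parameter on the baseline term.

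Three stronger readings are tempting, and the documents do not support them.

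- *The model will fail to converge.* An all-zero column is dropped and the treatment estimate is unaffected. With one baseline-TIPS subject, only that nuisance coefficient diverges; the separation does not reach the treatment coefficient. With two, separation is likely under the assumed rates but not certain. The right description is that the term is uninformative.
- *This is the only analysis that departs from the strata.* SAP 9.1.4 drops a stratum when it defines the subgroup, for good reason. SAP 9.1.3 includes an unstratified analysis, and the chi-square tests for refractory ascites (9.2.7) and ACLF (9.3.1) use neither stratum. What is particular to 9.3.10 is the mistaken reason and the conflict with the method it cites.
- *Eligibility makes the baseline term strictly empty.* SAP 12 says that earlier protocol versions allowed more than 3 days from screening to first dose, and those versions are not available to check. The documents support nearly empty, not empty.

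A reader might also infer that TIPS placed for any indication will be counted. The descriptive sentence in 9.3.10 is loosely worded, but the model's dependent variable is insertion for refractory ascites, so the text does not establish that.

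**Conclusion.** The point holds as a minor one. The reason in SAP 9.3.10 does not justify omitting history of hospitalization, and the omission contradicts the section's reference to 9.3.8. Both conclusions rest on the text alone. That the baseline term is nearly empty rests on the current eligibility and Day 1 rules.

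The numerical effect is small: at most 0.017 on a true odds ratio of 0.50 and 0.014 on 0.70. These figures depend on the assumed TIPS rates, history odds ratios and even split by history, none of which the documents give. No confirmatory conclusion is affected.

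**What to change.** In SAP 9.3.10, fit treatment, region and history of hospitalization for acute decompensation as in 9.3.8, using the IWRS values as 9.3.6 does. Delete the baseline-occurrence term and its definition, and delete the sentence explaining why history of hospitalization is left out. If sparse events were the real reason, say so and prespecify a penalized or exact method.

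The cost is a few lines of SAP text. The number of parameters does not change, because one term replaces another. The small downside is that the stratum parameter could be poorly estimated if very few TIPS events occur.
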